1 PROTOCOL SUMMARY

1.1 SYNOPSIS

Title:	Prospective Randomized Evaluation of 14F Thal Tube vs 28 French Chest Tube for Hemothorax and Use of Maximum Barrier Precautions
Phase:	Recruiting
Description of Sites/Facilities Enrolling Participants:	Carolinas Medical Center [name]
Study Description:	Traumatic hemothorax and hemopneumothorax are common diagnoses which are typically treated by placement of a chest tube. A retrospective review has previously shown equivalence between 14 Fr chest tubes and 32 – 40 Fr chest tubes for the non-emergent drainage of hemothorax; however, this study was not randomized. We seek to perform a prospective randomized trial that is adequately powered comparing efficacy of 14 Fr thal tubes to 28 Fr chest tubes for non-emergent drainage of hemothorax and hemopneumothorax. Additionally, we will employ maximal barrier precautions for all chest tube insertions and compare empyema rates to our historical controls for patients with hemothorax, hemopneumothorax, and pneumothorax.
Study Population:	Patients aged 18 and older diagnosed with a traumatic pneumothorax, hemothorax or hemopneumothorax that require non-emergent placement of a thoracostomy tube as part of their care.
Aims:	Aim 1: Determine the safety and efficacy non-inferiority between small bore (14 Fr) and large bore (28 Fr) in the drainage of traumatic hemothorax and hemopneumothorax Aim 2: Determine the incidence of empyema in the setting of traumatic pneumothorax, hemothorax and hemopneumothorax with the addition of maximum barrier precautions [Time Frame: 90 days]
Study Hypothesis	Aim 1: The investigators hypothesize that there is non-inferiority in safety and efficacy between the different chest tube sizes Aim 2: Maximum barrier precautions associated with a decrease in empyema rate.

[figure not shown]

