2.2 STUDY RATIONALE

Currently, there are no specific guidelines regarding the optimal chest tube size for the treatment of traumatic hemothorax or hemopneumothorax. The efficacy and safety of large bore tubes for pleural drainage is well documented and is considered standard practice⁷. While a randomized study comparing small vs. large bore chest tubes for pneumothorax has been performed the sample size was small and hemothorax was excluded⁸. The investigators have designed a large randomized clinical trial to address the limitations of the data regarding thoracostomy tube size in the treatment of traumatic hemothorax and hemopneumothorax. The investigators hypothesize that there is safety and efficacy non-inferiority between the different chest tube sizes (Aim 1).

In our previous retrospective study, we saw a decrease in empyema rates with 14 Fr catheters (small bore) for pneumothorax where the use of a large drape is standard of care for barrier protection. This prospective study, also seeks to determine the efficacy of the addition of maximal barrier precautions in the prevention of empyema for patients with hemothorax and/or pneumothorax (Aim 2).

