4 STUDY DESIGN

4.1 OVERALL DESIGN

The proposed study is a single center, prospective, non-inferiority trial evaluating the efficacy of small bore (14 Fr) vs large bore thoracostomy tubes in the setting of trauma at an American College of Surgeons designated Level I trauma center. Each patient will receive a study approved thoracostomy tube as indicated and our standard of care thoracostomy tube Practice Guideline will be followed. The study period is from the time of enrollment (visit day 0) up to 90 days (± 14 days) following the date of thoracostomy tube placement. A total of 645 subjects will be prospectively enrolled.

Aim I will be achieved through a prospective randomized study design which will evaluate thoracostomy tubes placed in the setting of traumatic hemothorax or hemopneumothorax. The efficacy of the thoracostomy tube sizes will be determined by assessing the participants for retained hemothorax which will be defined in this study as any residual blood that cannot be drained after 72 hours of thoracostomy as confirmed by imaging. A total of 252 subjects will be enrolled and randomized in this study group.

Aim II will be achieved through a prospective non-randomized controlled study design in which maximum barrier precautions will be used during chest tube placement for all prospective subjects diagnosed with a traumatic pneumothorax, hemothorax or hemopneumothorax. The prospective subjects will be compared to subjects in a retrospective analysis in which the use of maximum barrier precautions was not standard. Maximal barrier precautions will consist of a thyroid drape, hand hygiene, sterile gown, mask, and gloves. The use of sterile technique will be consistent throughout the prospective study. This will limit the variability between the two treatment arms and allow a more accurate comparison of empyema rates between tube size and sterile technique. The use of prophylactic antimicrobial agents will also be collected for these subjects. A total of 645 subjects will be enrolled in this study group (inclusive of those patients enrolled as part of Aim I).

All participants will be monitored for their need for operative intervention (e.g. VATS), development of empyema, hospital readmission, tube related complications (e.g. tube misplacement, tube migration), and death which occurs between thoracostomy tube placement and follow-up.

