9 STATISTICAL CONSIDERATIONS

9.1 STATISTICAL HYPOTHESES

Primary Efficacy Endpoint(s):

- Aim I
 - Retained hemothorax requiring an additional intervention, either video-assisted thoracoscopic surgery (VATS) or additional thoracostomy tube placement.
- Aim II
 - Empyema rates in traumatic pneumothorax, hemothorax, and hemopneumothorax

Secondary Efficacy Endpoint(s):

- Aim I
 - Duration of chest tube placement
 - Initial drainage from chest tube at 5 minutes
 - Length of hospitalization
 - Subjective pain score (pre- and post-insertion recorded within 5 minutes of insertion). Assessed with 0 -10 numerical pain scale
 - Hemodynamic stability post-insertion (determined by vital signs: temperature, heart rate, blood pressure, oxygen saturation)
 - Time to radiographic resolution of pneumothorax, hemothorax, hemopneumothorax
 - Tube specific complications: Air leak, tube malposition, & tube migration
 - Recurrent pneumothorax/hemothorax/hemopneumothorax after tube removal
 - Readmission to hospital for a chest tube related complication

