9.2 SAMPLE SIZE DETERMINATION

Aim I

This study is a non-inferiority randomized controlled trial comparing placement of 14 French vs. 28 French chest tubes for hemothorax and hemopneumothorax. We hypothesize the rate of drainage failure to be approximately 7% in the large 28 tube size group. With a sample size of n=126 per group, we will have 80% power to detect a non-inferiority margin difference between the group rates of 8% (allowing up to a 15% rate of drainage failure in the small 14 tube size group; $\alpha=0.05$). In our prior study, we saw a 20% vs 6.7% difference in needing additional procedures for pneumothorax with small vs large catheters but these numbers are based on draining air not blood. Sample size analyses were conducted in PASS 13⁹.

Aim II

Calculations of sample size were based on two-group comparisons of empyema rates. With assumptions of empyema rate is 5% in the retrospective group and 2% in the prospective group, 586 patients in each group are needed to achieve a power of 0.8 with $\alpha=0.05$. To account for potential attrition, we will inflate the number of patients by 10% resulting in a total of 645 patients in the retrospective group and 645 patients in the prospective group. The sample size was calculated by using the PASS 15¹⁰.

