9.4 STATISTICAL ANALYSES

9.4.1 GENERAL APPROACH

All analyses for this randomized trial will follow the intention to treat principle with an additional per protocol analysis given the non-inferiority hypothesis. We will first compare the baseline characteristics of the patients by group to assess for statistically significant or clinically meaningful imbalances. If either exists, these factors will be taken into account in sensitivity analyses for the primary and secondary outcomes.

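### Empyema is a primary endpoint with its own sample size, but no analysis is stated for its comparison with loosely specified historical controls, and Section 5.1 omits the pneumothorax patients that Aim II covers

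*Combined protocol and SAP*

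**What the plan says.** Section 4.1 describes Aim II as prospective, non-randomized and controlled: "The prospective subjects will be compared to subjects in a retrospective analysis in which the use of maximum barrier precautions was not standard". The synopsis says the trial will "compare empyema rates to our historical controls for patients with hemothorax, hemopneumothorax, and pneumothorax" and gives Aim 2 a 90-day time frame.

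Section 9.1 lists "Empyema rates in traumatic pneumothorax, hemothorax, and hemopneumothorax" under the primary efficacy endpoints. Section 9.2 adds "Calculations of sample size were based on two-group comparisons of empyema rates", assuming 5% in the retrospective group and 2% in the prospective group.

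Sections 9.4.1 to 9.4.4 and the statistics row of the synopsis cover drainage failure, length of stay, pain, vital signs, re-intervention, readmission and the interim looks. Neither empyema nor the prospective-versus-retrospective comparison appears. Section 9.4.1 opens "All analyses for this randomized trial will follow the intention to treat principle". On baseline imbalance it says: "If either exists, these factors will be taken into account in sensitivity analyses for the primary and secondary outcomes".

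On eligibility, Section 5.1 admits hemothorax and/or hemopneumothorax only. The synopsis criteria and Sections 4.1, 6.1 and 9.3 include pneumothorax, and Section 6.1 says how patients with suspected pneumothorax alone receive a tube.

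**The concern.** Aim II drives enrolment: 645 prospective patients are planned, of whom 252 serve Aim I. Section 2.2 says the study "seeks to determine the efficacy of the addition of maximal barrier precautions in the prevention of empyema". Yet the reader cannot tell which test will be run, on which effect measure, or with what adjustment.

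Because the controls are historical, differences other than barrier use can move the empyema rate. The documents point to several:

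- **Diagnosis.** The three diagnoses are named for both cohorts, but the control mix is not given.
- **Eligibility.** Section 5.2 excludes emergent placement and more than one tube. Nothing says the controls were selected in the same way.
- **Ascertainment.** Prospective patients get a Day 90 call that asks about readmissions, with empyema as an example (6.3). Nothing says the controls did. No empyema definition is given for either cohort.
- **Tube size and partial barrier use.** Section 2.2 reports "a decrease in empyema rates with 14 Fr catheters (small bore) for pneumothorax where the use of a large drape is standard of care", so both may already have varied among past patients.

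Section 5.1 adds to the uncertainty, because read literally it changes the diagnosis mix of the prospective cohort. At stake is whether an observed fall in empyema can be credited to barrier precautions, and whether a real fall could be masked.

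**Working it through.** **1. The plan's own figure.** Inputs from 9.2: 5% and 2%, power 0.80, α = 0.05 (sidedness not stated). Unpooled normal approximation, two-sided:

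n = (1.96 + 0.842)² × (0.05×0.95 + 0.02×0.98) / 0.03² = (1.96 + 0.842)² × (0.0475 + 0.0196) / 0.0009 = 585.2, so 586 per group.

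This reproduces; a one-sided test would give 461. Then 586 × 1.10 = 644.6, so 645. The sample size therefore rests on an unadjusted, two-sided comparison of two proportions. That is an inference from the arithmetic, not a stated analysis.

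**2. One illustration of case mix.** The assumptions, none of them documented, are:

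- empyema risk of 2% with pneumothorax only and 7% with any hemothorax;
- no barrier effect;
- prospective hemothorax share 252/645 = 0.391, if all others have pneumothorax only;
- control hemothorax share 0.60, chosen because it returns the plan's 5%;
- 586 per group.

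Expected rates:

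- Controls: 0.40×0.02 + 0.60×0.07 = 0.050
- Prospective: 0.609×0.02 + 0.391×0.07 = 0.0395

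The apparent reduction of 1.05 percentage points is due to mix alone. The pooled rate is 0.0448, and the standard error is √(0.0448×0.9552×2/586) = 0.0121. The expected z is 0.0105/0.0121 = 0.87. The chance of a significant decrease is Φ(0.87 − 1.96) ≈ 0.14; exact enumeration gives 0.136, against a nominal 0.025. A Mantel-Haenszel test stratified by diagnosis, simulated under the same assumptions, gives about 0.025.

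**3. Where there is no bias.** With a 4% risk for both diagnoses, the unadjusted test gives 0.025 whatever the mix. If the controls have the smaller hemothorax share and hemothorax carries the higher risk, the bias runs the other way and hides a real reduction.

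**4. What stratifying by diagnosis does not remove.** Suppose background risk is 20% lower in the prospective period for other reasons and barriers do nothing. Take assumed risk ratios of 2:7 or 3:6, scaled to a 5% control rate, and control hemothorax shares of 20-80%. The stratified test still declares a decrease about 10-14% of the time at 586 per group.

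**5. Power of the stratified test.** Under the same scaling, with the plan's effect (relative risk 0.02/0.05 = 0.4), power at 586 per group is about 0.65-0.85 across control shares of 20-80%. In the illustration of step 2 (60% share) it is 0.74. Exact power of the unadjusted test for 5% against 2% is 0.81.

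**The case against.** **The imbalance clause in 9.4.1 might be read to cover Aim II.** It sits under a sentence about the randomized trial. Even if it applied, it is conditional, names no covariate or method, and leaves the primary comparison unadjusted.

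**Aim II is modestly worded.** Its objective is to determine incidence, and the synopsis hypothesis speaks of an association. This stands, and the conclusion should keep to it. But Section 2.2 speaks of efficacy, and a powered comparison of a primary endpoint still needs a stated analysis.

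**The bias figures are assumed.** They are. No section gives empyema by diagnosis or the control mix. The documents also do not say whether hemothorax patients continue to be enrolled once 252 are randomized, so the 39% share is itself an assumption. Larger error rates follow from more extreme mixes, but at an 80% control share the assumed rates imply 0.2×0.02 + 0.8×0.07 = 6% in controls, not the planned 5%.

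**Section 5.1 looks like a drafting slip.** Agreed. A reader might infer that Aim II can enrol only hemothorax patients, or only 252 of them. The documents do not support either as the operating plan: the synopsis, 4.1 and 9.3 include pneumothorax, 6.1 gives its handling, and 5.1 sets no cap at 252. The conflict needs reconciling, not a power calculation.

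**Missed empyemas in controls would work against the hypothesis.** Correct: they would make a benefit harder to show and could not create a false one.

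**Mantel-Haenszel is one choice among several.** Also correct. The need is for a named analysis adjusted for diagnosis.

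**Conclusion.** The concern holds in this form. A primary endpoint with its own sample size has no stated analysis, and the only method indicated is an unadjusted comparison with non-randomized historical controls whose selection and follow-up are not described. Section 5.1 contradicts the population on which Aim II is defined. These points rest on the text alone.

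The possible size of the bias rests on assumptions. The illustration gives about 14% false significant decreases unadjusted, about 2.5% stratified, and no bias if risk is the same in both diagnoses.

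Three stronger readings are tempting but not supported:

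- **That the Aim II comparison is biased.** The documents show only that it could be.
- **That the earlier retrospective study in 2.2 supplies the controls.** This is not stated.
- **That adjusting for diagnosis would make the result causal.** Drift over time would remain.

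The randomized Aim I comparison is not affected. The change should be made before the cohorts' outcomes are compared.

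**What to change.** 1. Reconcile Section 5.1 with the synopsis and Sections 4.1, 6.1 and 9.3.
2. Add an Aim II subsection to 9.4. Make the primary comparison adjusted for diagnosis, for example Mantel-Haenszel with two strata (pneumothorax only; any hemothorax). Report the risk difference with its 95% CI, and the unadjusted and stratum-specific rates beside it. Pre-specify sensitivity analyses for tube size, injury severity and antibiotics, as far as event numbers allow.
3. State one empyema definition. Apply it, the 90-day window and the clinical eligibility criteria that can be applied retrospectively (no emergent placement, no multiple tubes) to the controls. Criteria such as investigator-witnessed placement and consent cannot be carried back. Add a sensitivity analysis restricted to record-detected empyema in both groups.
4. State the controls' calendar period, show empyema rates by calendar time, and word the conclusion as an association.
5. Restate Aim II power for the adjusted analysis once the control mix is known and before outcomes are compared.

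**Cost.** Protocol and SAP wording, plus chart abstraction for controls. Diagnosis and injury severity are already baseline items for prospective patients (6.2), and antimicrobial use is collected (6.5). Some power may be lost: about 0.65-0.85 at 586 per group under the assumptions in step 5 of the working, against the planned 0.80. Under the assumed rates the 95% CI half-width changes by about −0.1 to +0.1 percentage points, or up to about +0.3 with no effect and an 80% control hemothorax share.

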4.2 SCIENTIFIC RATIONALE FOR STUDY DESIGN

There is currently not enough evidence in the literature to know which size chest tube is best in this patient population, which is a primary purpose of the study.

4.3 END OF STUDY DEFINITION

The study will be complete once target enrollment has been achieved and all outcomes information is available.

5 STUDY POPULATION

5.1 INCLUSION CRITERIA

- The patient is admitted to the trauma service.
- The patient has a hemothorax and/or or hemopneumothorax, requiring thoracostomy tube placement.
- Thoracostomy tube placement is able to be performed or witnessed by an investigator listed on the study.
- The patient has not had a chest tube in the past year.
- The patient is ≥ 18 years of age.
- In the event the patient is decisionally impaired, consent will be obtained from the individual's legally authorized representative (LAR) or from the individual's healthcare power of attorney (HPA).
- In the instance of reversible impairment, initial consent would be obtained from the LAR/HPA and the patient will be approached for consent once he/she is deemed mentally competent by the care provider.

5.2 EXCLUSION CRITERIA

- The patient is incarcerated
- The patient is known to be pregnant
- The patient is hemodynamically unstable, requiring emergent chest tube placement (in <10 minutes from evaluation).
- The patient will have more than one chest tube placed at the time of enrollment.

5.3 SCREEN FAILURES

Screen failure patients for this study are those who choose to withdraw from the study or who are discovered to meet exclusion criteria after enrollment.

5.4 STRATEGIES FOR RECRUITMENT AND RETENTION

Subject enrollment will take place at a single American College of Surgeons designated Level I trauma center. A partial waiver of authorization will be requested for the purposes of pre-screening for enrollment via electronic medical record review. All patients 18 years of age and older sustaining trauma that requires therapeutic tube thoracostomy will be screened for study eligibility by the research staff. Participants will be approached for consent as soon as it has been determined that the patient has met all inclusion criteria and no exclusion criteria.

The study design aims to maintain high patient retention throughout the study period. Subject retention strategies include limiting study involvement to three months and limiting subject follow-up to electronic medical record review supplemented by a single telephone call.

6 STUDY INTERVENTION

6.1 STUDY INTERVENTION(S) ADMINISTRATION

Screened subjects eligible for study participation will have their inclusion/exclusion criteria verified by an investigator. The subject will be approached for consent by the research staff and enrolled. Subjects with suspected pneumothorax alone will receive either a small bore (14 Fr) or large bore (28 Fr) tube chosen based on physician preference. Subjects with suspected hemothorax or hemopneumothorax will be randomized to receive either a small or large bore chest tube.

Enrolled subjects will have their thoracostomy tube placement procedure observed and verified by an investigator listed on this protocol. The training level of the individual performing the procedure will be recorded. Maximum barrier precautions for this study will be used during the placement procedure for all prospective subjects. Maximum barrier precautions for this study will be defined as the correct use of proper hand hygiene, a cap, surgical gown, sterile gloves, mask, and a thyroid drape. The institutional standard of care thoracostomy tube Practice Guidelines will be followed.

6.2 INDEX HOSPITALIZATION REVIEW

At the time of enrollment, baseline demographic and injury characteristics will be recorded. Baseline data to be recorded include:

- Demographics (age, sex)
- Vital signs (pre- and post-tube insertion)
- Mechanism of injury (blunt vs penetrating)
- Radiographic findings (pneumothorax, hemothorax or hemopneumothorax)
- Initial laboratory values (hematologic panel, chemistry panel, coagulation panel, toxicology, blood gases)
- Calculated injury severity score

The day of tube insertion will mark study day 0. Subjects will be monitored daily by study staff in the form of chart review for the duration of their hospitalization. A daily data log will be kept for each patient/ The information to be recorded includes:

- Volume of hemo/hemopneumothorax drainage
- Tube misplacement
- Tube migration
- Presence of air leak
- Need for additional thoracostomy tubes

- Need for operative intervention (VATS, thoracotomy)
- Date and time of pneumo/hemo/hemopneumothorax resolution as confirmed by a radiologist
- Date and time of chest tube removal
- Recurrent pnemo/hemo/hemopneumothorax
- Development of infection

6.3 THREE (3) MONTH FOLLOW-UP (DAY 90±14)

Each participant will be followed for three months (90 days). Participants will receive a telephone follow-up on day 90 (+/- 2 weeks). Information obtained during the call will include: survival, adverse events and readmission to any hospital for complications related to chest tube placement (e.g. empyema, re-accumulation/recurrent pneumo- or hemothorax, fibrothorax).

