7.3 LOST TO FOLLOW-UP

At Day 90 a telephone call will be made to the participant to assess outcome. Three attempts will be made to establish contact. If contact is not achieved, the electronic medical record will be the only source used to complete the data set.

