10.1.4 KEY ROLES AND STUDY GOVERNANCE

Principle Investigator- The investigator is responsible for ensuring that the clinical study is performed in accordance with the protocol, current ICH GCP guidelines, the Declaration of Helsinki and applicable institutional regulatory requirements.

Medical Monitor (MM)- The MM will provide medical guidance and oversee the safety aspects of the study. The MM is responsible for monitoring serious adverse events (SAEs) on an ongoing basis to ensure participant safety.

Quality Assessment Nurse - The quality assessment nurse will review patient enrollment weekly and provide a secondary point of review to monitor patients for significant chest tube related complications (e.g. ICU re-admissions, hospital re-admissions, re-current pneumothoraces/hemothoraces, etc.). All complications reported by the patient or staff will be reported to the quality assessment nurse.

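### Aim II counts post-discharge empyemas reported by telephone in the prospective cohort, while no matching source, case definition or 90-day window is stated for the retrospective cohort

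*Combined protocol and SAP*

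**What the plan says.** Section 9.1 lists the empyema rate as the primary efficacy endpoint of Aim II, and the synopsis gives Aim 2 a 90-day time frame. Section 4.1 sets the comparison: "The prospective subjects will be compared to subjects in a retrospective analysis in which the use of maximum barrier precautions was not standard". The synopsis calls the comparator historical controls. Neither place says from which sources, over what window or by what definition empyema was identified in that group.

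For the prospective cohort the sources are described:

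- In hospital (6.2): "Subjects will be monitored daily by study staff in the form of chart review for the duration of their hospitalization". The daily log includes development of infection.
- Schedule of Activities (1.3): assessment for empyema and fibrothorax continues to day 90.
- After discharge (5.4 and 6.3): record review plus one telephone call at day 90 ± 14. The call asks about survival, adverse events and "readmission to any hospital for complications related to chest tube placement (e.g. empyema, re-accumulation/recurrent pneumo- or hemothorax, fibrothorax").
- If three call attempts fail (7.3): "If contact is not achieved, the electronic medical record will be the only source used to complete the data set".
- Quality assessment nurse (10.1.4): to "provide a secondary point of review to monitor patients for significant chest tube related complications".

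Section 9.4 contains no analysis method for Aim II and no comparison limited to sources that both cohorts share.

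**The concern.** A difference between two cohorts can be read as an effect of barrier precautions only if an empyema of the same kind has the same chance of being counted in each. Followed as written, the plan counts an empyema treated at another hospital and learned of by telephone in the prospective cohort. Nothing described for the retrospective cohort would find the same event. Within the prospective cohort, too, the source depends on whether the participant answers the telephone.

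Fuller capture on the prospective side raises that cohort's observed rate relative to the controls and shrinks an apparent fall. Adjustment for patient mix cannot repair this, because the events at issue were never recorded. Aim II sets the prospective enrolment of 645, so a muted contrast would weaken the comparison for which most of the recruitment is planned.

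**Working it through.** **Inputs from section 9.2.** Rates: "With assumptions of empyema rate is 5% in the retrospective group and 2% in the prospective group". Size: the stated requirement is 586 per group for 80% power, with α = 0.05 (sidedness not stated) and 10% inflation to 645 per group.

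**Input assumed.** s = the fraction of empyemas that records capture, relative to the prospective methods. The documents give no value; 0.9, 0.8 and 0.7 are shown.

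**Step 1: reproduce the plan's figure.** Two-sided, unpooled variance:

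n = (1.960 + 0.842)² × (0.05×0.95 + 0.02×0.98) / 0.03² = 7.849 × 0.0671 / 0.0009, which rounds up to 586.

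The pooled version gives 588. One-sided versions without continuity correction give 461 to 463, so the plan is two-sided. Inflation: 586 × 1.1 = 644.6, so 645. The stated sample size stands.

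**Step 2: power formula.** With p̄ = (p₁+p₂)/2,

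power = Φ{ [ |p₁−p₂|√n − 1.960√(2p̄(1−p̄)) ] / √(p₁(1−p₁)+p₂(1−p₂)) }.

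- 5% v 2%, n = 586: Φ(0.837) = 0.799.
- 5% v 2%, n = 645: Φ(0.975) = 0.835.

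**Step 3: unequal capture, 645 per group.** Section 9.2 does not say whether 5% is a true rate or the rate that records show, so both readings are run.

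- Reading A: 5% is the true control rate and records show 5% × s; the prospective 2% is fully seen. At s = 0.8, 4.0% v 2.0% gives Φ(0.146) = 0.558.
- Reading B: 5% is already records-based, and 2% is what the same records would show prospectively; fuller capture shows 2%/s. At s = 0.8, 5.0% v 2.5% gives Φ(0.404) = 0.657.

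| s | A: rates | A: power | B: rates | B: power |
|---|---|---|---|---|
| 1.0 | 5.0 v 2.0% | 0.835 | 5.0 v 2.0% | 0.835 |
| 0.9 | 4.5 v 2.0% | 0.717 | 5.0 v 2.2% | 0.763 |
| 0.8 | 4.0 v 2.0% | 0.558 | 5.0 v 2.5% | 0.657 |
| 0.7 | 3.5 v 2.0% | 0.377 | 5.0 v 2.9% | 0.508 |

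**Step 4: allow for unanswered calls.** Reading A treats the prospective rate as fully ascertained, but section 7.3 leaves unreached participants with the record alone. If 70% are reached (assumed), the prospective rate is 2% × (0.7 + 0.3s) = 1.94%, 1.88% or 1.82%. Power under reading A at 645 is then 0.741, 0.616 or 0.466.

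**Step 5: the shared-source comparison, 645 per group.** If records see a fraction s in both cohorts, the rate ratio is preserved. At s = 0.8, 4.0% v 1.6% gives Φ(0.654) = 0.744.

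| s in both cohorts | rates | power | n per group for 80% |
|---|---|---|---|
| 0.9 | 4.5 v 1.8% | 0.793 | 656 |
| 0.8 | 4.0 v 1.6% | 0.744 | 741 |
| 0.7 | 3.5 v 1.4% | 0.685 | 850 |

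These rows match reading A. Under reading B the shared-source contrast is 5% v 2% itself, and power stays at 0.835.

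**The case against.** The strongest reply is that the plan never says how control empyemas were found. A reader might infer that they come only from old records, with no telephone contact. The words retrospective and historical suggest this, but no section states it, and section 2.2 mentions an earlier retrospective study without its methods. This stands. What can be said is that no counterpart to the call is described.

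A reader might also set daily surveillance against chart review. Section 6.2 says the daily monitoring is chart review, no extra imaging or culture is specified for it, and the examples given for the nurse's review do not name empyema. This stands too: the in-hospital gap may be small, and the point is confined to events after discharge or at other hospitals. Even there, section 7.3 does not say whether the electronic record shows care given elsewhere.

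Finally, this bias runs toward no effect, so by itself it would not create a false claim of benefit. Time trends and case mix can act in either direction, so the net bias is unknown. That limits what may be concluded, but it is no reason to leave a removable bias in place in the hope that others offset it.

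**Conclusion.** The point holds for post-discharge and outside-hospital empyema: one cohort has a described route by which such events enter the count, the other has none, and no common definition, source or window is stated. The planned sample size is correctly calculated; the defect lies in comparability of measurement.

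At 645 per group, assumed relative capture of 90%, 80% or 70% lowers power from 84% to 72%, 56% or 38% if 5% is the true control rate, or to 76%, 66% or 51% if it is already records-based. Unanswered calls soften the first set. These figures illustrate sensitivity to an unknown quantity and do not estimate the actual loss.

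Two stronger readings are not supported. The documents do not show that the comparison as a whole is biased toward no effect, because other features of a historical comparison may act the other way. Nor do they say that the 90-day window was chosen because empyema tends to appear after discharge; they give only the time frame.

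**What to change.** In sections 4.1, 6.3 and 9.1, define the main Aim II between-cohort comparison as empyema documented in the study hospital's electronic medical record within 90 days of tube insertion, using one written case definition and the same abstraction form in both cohorts. Record the source of each empyema. Report call-only and outside-hospital empyemas in the prospective incidence and safety results and as a sensitivity analysis, but leave them out of the main comparison. If the controls did have an equivalent source after discharge, state it.

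The cost is wording, one form and one data field; no visits or staff are added, since the record is already reviewed for prospective participants. There is a statistical cost: if records capture 90%, 80% or 70% of cases in both cohorts, power at 645 per group is about 79.3%, 74.4% or 68.5%, and 80% power would need 656, 741 or 850 per group. That is still better than unequal capture of the same size under reading A. The change does not remove any extra charting prompted by trial attention, including the nurse's review.
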